10.1.2 Evaluable for Radiation Site Progression Free Survival (RSS PFS)

All patients who have received at least one dose of radiotherapy and have an MRI of entire spine at baseline and at least the 3 month follow up contact will be considered evaluable for RSS PFS. Patients will have RSS PFS assessed as described below in Section 10.2.3.

10.1.3 Evaluable for the Spinal Instability Analysis

All patients who have had their baseline SINS score and at least one follow-up SINS score (at either 3 and/or 6 months) assessed will be considered evaluable for the spinal instability analysis.

10.1.4 Evaluable for Adverse Events

All patients will be evaluable for adverse event evaluation from the time of their first treatment with CRT or SBRT.

10.1.5 Evaluable for Quality of Life Assessment

All patients who have completed a baseline quality of life questionnaire (EORTC QLQ-C30 and QLQ-BM22) and at least one follow-up questionnaire are evaluable for quality of life assessment.

10.1.6 Evaluable for Economic Analysis

All patients who have completed a baseline economics analysis questionnaire (EQ-5D-5L) and at least one follow-up questionnaire are evaluable for economic analysis.

10.1.7 Evaluable for Radiotherapy Quality Assurance (RTQA) Compliance

Canadian and Australian centres will be evaluable for RTQA compliance from the time they are locally activated to participate on the study.

10.2 Definitions

10.2.1 Response Outcomes

Pain response to radiotherapy is based on the International Bone Metastases Consensus Endpoint definitions [Chow 2002].

Complete Pain Response:

A Complete Pain Response is defined as a pain score of zero (0) at the treated site with no concomitant increase in analgesic intake (stable or reducing analgesics in daily oral morphine equivalent)

Partial Pain Response:

Partial response is defined as any of the following:

- i. Reduction in worst pain score of two or more at the bony metastatic site on a 0–10 scale without analgesic increase.
- ii. Analgesic reduction of 25% or more from baseline without an increase in worst pain score with reference to baseline.
- iii. For patients who were using opioid analgesics at the baseline assessment, a daily oral morphine equivalence of zero (0) without an increase in worst pain score relative to the baseline worst pain score.

Pain Progression:

Pain progression is defined as any of the following:

- i. An increase in worst pain score of two or more points above baseline at the treated site without reduction of analgesic use.
- ii. An increase of 25% or more in daily oral morphine equivalent compared with baseline, without reduction in worst pain score.
- iii. For patients who were not using opioid analgesics at the baseline assessment (daily oral morphine equivalence = 0), consumption of any opioid analgesic without a reduction in worst pain score relative to the baseline worst pain score.

Stable Pain:

Stable pain (SD) is assigned to the remaining evaluable patients, who do not meet any of the categories of Complete/Partial Response and Pain Progression.

10.2.2 Radiation Site Progression Free Survival (RSS PFS)

Radiation site progression free survival is defined as the time from randomization to local progression or death.

The response assessment will be an investigator interpretation of the following criteria: lesion status, size, epidural disease extent (Bilsky scale and 3 D measurements), degree of angular kyphosis and height of vertebral body [[name] 2015].

Local progression may be defined as:

- Gross unequivocal increase in tumor volume or linear dimension.
- Any new or progressive tumor within the epidural space.
- Neurologic deterioration attributable to pre-existing epidural disease with equivocal increased epidural disease dimensions on MRI.

Biopsy is recommended in those situations in which pseudoprogression due to radiation reaction cannot be ruled out.

10.2.3 Overall Survival

Overall survival is defined as the time interval between the date of randomization and the date of death from any cause. Patients who are still alive at the time of the final analysis or who have become lost to follow-up will be censored at their last date known to be alive.

11.0 SERIOUS ADVERSE EVENT REPORTING

This protocol does not contain investigational agent(s), and adverse events occurring as a result of radiotherapy treatment should be reported to CCTG in the manner described below. In addition, your local Research Ethics Board (REB) should be notified.

The descriptions and grading scales found in the NCI Common Terminology Criteria for Adverse Events (CTCAE) will be utilized for Adverse Event (AE) reporting (version can be found in Appendix V). All appropriate treatment areas should have access to a copy of the CTCAE. A copy of the CTCAE can be downloaded from the CTEP web site:

(http://ctep.cancer.gov/protocolDevelopment/electronic_applications/ctc.htm).

All serious adverse events (SAE) defined as per ICH guidelines (see below) and other adverse events must be recorded on case report forms. In addition, all “reportable” serious adverse events are subject to expedited reporting using the CCTG SAE form. The term ‘reportable SAE’ is used in the definitions which follow to describe those SAEs which are subject to expedited reporting to CCTG.

11.1 Definition of a Reportable Serious Adverse Event

- All serious adverse events which are unexpected and related to protocol treatment must be reported in an expedited manner (see Section 11.2 for reporting instructions). These include events occurring during the treatment period (until 30 days after last protocol treatment administration) and at any time afterwards.
- Unexpected adverse events are those which are not consistent in either nature or severity with information provided in section 3.
- Adverse events considered related to protocol treatment are those for which a relationship to the protocol treatment cannot reasonably be ruled out.
- A serious adverse event (SAE) is any adverse event that at any dose:
 - results in death
 - is life-threatening
 - requires inpatient hospitalization or prolongation of existing hospitalization (excluding hospital admissions for study drug administration, transfusional support, scheduled elective surgery and admissions for palliative or terminal care)
 - results in persistent or significant disability or incapacity
 - is a congenital anomaly/birth defect

Medical and scientific judgement should be exercised in deciding whether expedited reporting is appropriate in other situations such as important medical events that may not be immediately life-threatening or result in death or hospitalization but may jeopardize the patient or may require intervention to prevent one of the events listed above.

11.2 Serious Adverse Event Reporting Instructions

All reportable serious adverse events must be reported using a web-based Electronic Data Capture (EDC) system being used for this trial. For details about accessing the EDC system and completing the on-line SAE report form, please refer to the CCTG Generic Data Management Guidebook for EDC Studies posted on the SC.24 section of the CCTG website (www.ctg.queensu.ca).

Within 24 hours: Complete preliminary Serious Adverse Event Report and submit to CCTG via EDC system.

Within 10 days: Update Serious Adverse Event Report as much as possible and submit report to CCTG via EDC system.

EDC SAE web application interruption:

In the rare event that internet connectivity to the EDC SAE system is disrupted, please print and complete a paper copy of the SAE Report, available from the trial specific website

FAX paper SAE Report to:

SC.24 Study Coordinator
Canadian Cancer Trials Group
[contact]

Please use the same timelines for submission as for direct EDC reporting.

Once internet connectivity is restored, the information that was FAXED to CCTG on the paper SAE Report must also be entered by the site into the EDC SAE web application.

Local internet interruption:

If you are unable to access the EDC SAE system, and cannot access a paper copy of the SAE Report from the trial website, please phone the SC.24 trial team [contact]) to obtain a copy of the SAE Report by FAX. Once completed, the report must be FAXED back to CCTG as indicated above. Once internet connectivity is restored, the information that was FAXED to CCTG on the paper SAE Report must also be entered by the site into the EDC SAE web application.

In cases of prolonged internet interruptions, please contact the CCTG Safety Desk for further instructions [contact]).

11.3 Other Protocol Reportable Events – Pregnancy Reporting

11.3.1 Pregnancy Prevention

Women of Child bearing Potential (WOCBP) and males who are enrolled in the trial must have agreed to use contraceptive method(s) as described in Eligibility Criterion 5.1.12. Investigators may wish to additionally advise the female partners of male participants about pregnancy prevention guidelines when appropriate and compliant with local policy.

11.3.2 Pregnancy Reporting

The investigator is required to report to CCTG any pregnancy occurring in female participants or female partners of male participants during treatment. Pregnancies occurring up to 6 months after the completion of radiotherapy must also be reported.

The investigator should report the pregnancy in a timely manner, within 24 hours of learning of the pregnancy using the CCTG Pregnancy Reporting Form, available from the trial webpage.

AMEND #1: 2017-FEB-02

Once informed consent has been obtained, the form should be updated to provide further pregnancy information and to reflect the outcome of the pregnancy. All follow-up reports must be submitted to CCTG in a timely manner. For pregnant partner of trial participant (and pregnant participants, if required by local policy), a copy of the signed signature page of the pregnancy follow-up consent must be submitted to CCTG.

Documents outlined above (including updates) must be sent to the CCTG safety desk [contact]/ [contact]).

If the pregnancy results in death (e.g. spontaneous abortion, stillbirth); is life-threatening; requires inpatient hospitalization or prolongation of existing hospitalization; results in persistent or significant disability/incapacity; is a congenital anomaly/birth defect, then an SAE report must be additionally submitted as described above. Please note, hospitalization for labour/delivery alone does not constitute an 'inpatient hospitalization' for the purposes of pregnancy reporting.

11.4 CCTG Responsibility for Reporting Serious Adverse Events to Health

The CCTG will provide expedited reports of SAEs to Health Canada for those events which meet regulatory requirements for expedited reporting, i.e. events which are BOTH serious AND unexpected, AND which are thought to be related to protocol treatment (or for which a causal relationship with protocol treatment cannot be ruled out).

11.5 Reporting Serious Adverse Events to Investigators

CCTG will notify Investigators of all serious adverse events from this trial that are reportable to regulatory authorities in Canada as reported to CCTG. This includes all serious events that are unexpected and related (i.e. possibly, probably, or definitely) to protocol treatment. The reports will be posted to the CCTG trial SC.24 web-based safety monitoring utility.

Investigators must notify their Research Ethics Boards (REBs) of events which involve corrective action(s) to be taken as a result of the event(s) such as protocol and/or informed consent changes. The date of REB Submission for these SAEs will need to be entered into the CCTG trial SC.24 web based safety monitoring utility and documentation of REB submission must be retained in the study binder on site. The REB submission template provided by CCTG can be used to assist with tracking, submission, filing and monitoring.

The submission of events to your ethics board should be done as soon as possible (we suggest within 30 days). REB submissions greater than 90 days from the date of notification will be regarded as delinquent and a major deficiency will be assigned. These safety reports are to be filed in the trial files on site.

12.0 PROTOCOL TREATMENT DISCONTINUATION AND THERAPY AFTER STOPPING

12.1 Criteria for Discontinuing Protocol Treatment

Patients may stop protocol treatment in the following instances:

- Intercurrent illness which would, in the judgement of the investigator, affect assessments of clinical status to a significant degree, and require discontinuation of protocol therapy.
- Unacceptable toxicity (see also Sections 3.1.1.1 or 3.1.2.1).
- Investigator discretion
- Request by the patient.
- Completion of therapy as outlined in Section 8.0. Efforts should be made to maintain the investigations schedule and continue follow-up, even if patients discontinue protocol treatment prematurely and/or no longer attend the participating institution.

12.2 Therapy After Protocol Treatment is Stopped

After protocol radiotherapy is completed, further treatment is at the discretion of the investigator. However, according to Section 5.2.5 patients are not expected to receive chemotherapy within one week of completing protocol radiotherapy.

12.3 Follow-up Off Protocol Treatment

All patients will be followed until 6 months after the end of radiotherapy.

13.0 CENTRAL REVIEW PROCEDURES AND SPECIMEN COLLECTION

13.1 Radiotherapy Quality Assurance (RTQA)

RTQA, consisting of (1) credentialing at the investigator level and prior to centre local activation, (2) prospective centre-based review of treatment plans prior to start of radiotherapy for every patient randomized on the study, (3) retrospective external review for all patients after completion of radiotherapy, and (4) planning MRI and dosimetry data submission for quality assurance review, will be required for all patients randomized to the study. See section 8.4 and the SC.24 RTQA Manual posted on the trial webpage for details.

13.2 Central Radiology Review

Central radiology review for the purposes of the radiation site progression-free survival (RSS PFS) secondary endpoint will be required for all patients randomized to the study. The central reviewer will be blinded to study radiotherapy treatment allocation. Please see the SC.24 trial webpage (www.ctg.queensu.ca) for details of electronic upload of MRI files.

13.3 Central Pathology Review

There will be no central pathology review for this study.

13.4 Specimen Collection

The collection of blood is an important part of this trial. Blood will be carefully banked as part of the CCTG tissue bank at Queen's University in Kingston, Ontario.

The blood may be used by researchers now or in the future to develop predictive biomarkers for SBRT. Samples will be used for research purposes only and will not be sold. A scientific review process of any proposals to use the blood will take place and any proposals approved will have undergone ethics approval. Patients will not be identified by name. The only identification will be by a patient study number assigned at the time of randomization to the trial and patient initials. Material issued to researchers will be anonymized and only identified by a coded number.

All patients on whom a blood sample is collected will be aware of this retrieval and will have given their consent.

There will be no specimen collection kits provided for this study. Red topped tubes will be used to collect serum and EDTA-lavender topped tubes will be used to collect plasma.

Specimens will be stored at participating centers at -80°C immediately after collection and then batch-shipped (i.e. multiple samples from one site in one shipment) to the CCTG Tissue Bank, frozen on dry ice, for subsequent storage and ultimate analysis. A Specimen Submission Form should accompany all shipments. Details of specimen, collection, processing, packaging and shipping (including the Specimen Submission Form) can be found in the SC.24 Specimen Collection Manual that is posted on the trial webpage.

AMEND #1: 2017-FEB-02; AMEND #2: 2018-APR-03; AMEND #3: 2018-OCT-31

14.0 STATISTICAL CONSIDERATIONS

14.1 Objectives and Design

This study is a randomized multicentre phase II/III study.

The primary endpoint of the phase II study is feasibility of accrual patients to the study, which is defined as the ability to accrue 54 patients over an 18-month period to a study that randomizes patients with spinal metastases to Stereotactic Body Radiotherapy (SBRT) or Standard Conventional Radiotherapy (CRT) within a Canadian multicentre setting.

The primary endpoint of the phase III study is the complete pain response rate at 3 months post-radiation.

Secondary Endpoints:

- Complete pain response in the treatment area at 6 months post-radiation
- Radiation site progression-free survival (RSS PFS) at 3 and 6 months
- SINS score at 3 and 6 months
- Overall survival
- Adverse event profile
- Health-related Quality of Life
- Radiotherapy Quality Assurance (RTQA) compliance

14.2 Primary Endpoints and Analysis

The primary endpoint of the phase II study is feasibility which is defined as the ability to accrue 54 patients over an 18 month period to a study that randomizes patients with spinal metastases to Stereotactic Body Radiotherapy (SBRT) or Standard Conventional Radiotherapy (CRT) within a Canadian multicentre setting.

The primary endpoint of the phase III study is the complete pain response at 3 months post-radiation, which is defined as in section 10.2.1. The analysis of the primary outcome will be based on the intent-to-treat principle, which will include all randomized patients, regardless of whether radiation therapy is given, given as per protocol, or whether there has been fidelity to treatment allocation. Patients that are inevaluable for the primary endpoint due to missing data will be considered as non-responder for the intent-to-treat analysis of the primary endpoint. The primary test will be the Cochran-Mantel-Hanzeal test stratified by baseline stratification factors of Histology (radioresistant vs. radiosensitive) and “Mass” on imaging (present vs. absent), a Chi-square analysis will also be applied to test the complete pain response rates between the two arms, and the 95% confidence limits of the rate difference between the two arms will be evaluated. Logistic regression will be used to estimate the treatment effect while adjusting for unbalanced important factors and to explore factors that are predictive of the complete pain response.

AMEND #1: 2017-FEB-02; AMEND #2: 2018-APR-03; AMEND #3: 2018-OCT-31

14.3 Sample Size and Duration of Study

For the randomized phase II portion of the study, a convenience sample size of 54 patients is considered sufficient to evaluate whether accrual is feasible. This sample size would also provide an opportunity to estimate the CRT and SBRT 3 month complete pain relief response rates, which would provide the basis for the sample size calculation of the future randomized controlled trial. We chose a sample size that provides for standard error rates in both treatment arms to be less than 10%. Assuming that the CRT response rate is 10% to 30%, with 27 patients, the standard error for the estimated response rate will be 5.8% to 8.8%, respectively. Assuming that the SBRT response rate is about 30% to 50%, with 27 patients, the standard error for the estimated response rate would be 8.8% to 9.8%, respectively.

The trial was activated in July 2015. By November 2016, 44 patients had been enrolled onto the study and the accrual rate indicated that the sample size would be reached in 18 months, thereby meeting the primary objective of the phase II feasibility study. Other metrics of trial conduct were examined including treatment related toxicity and tolerability as well compliance with radiotherapy including quality assurance measures. No safety signals were detected in either arm. Notably, spinal fracture within the treatment fields occurred in 2 patients - both on the conventional treatment arm (CRT). Compliance with protocol mandated radiotherapy and quality assurance measures was high.

Based on the demonstration of feasibility of trial conduct and continued need to critically evaluate the efficacy of SBRT in the treatment of painful spinal metastases, approval was sought and granted in January 2017 for conversion of the study design from a randomized phase II feasibility study to a randomized phase II/III study comparing the two radiotherapy treatment strategies.

Sample size estimate for the phase III controlled trial is with a two-sided 5% level test and 80% power. Based on the results of a randomized phase II trial [*Sprave 2018*] with similar enrollment and radiobiology criteria as the current study, we estimate the complete pain responses will be 20% for the CRT and 40% for the SBRT treatment arms, respectively.

Assuming a 15% drop out/inevaluable rate, we expect the complete pain response rates for the intent-to-treat analysis to be 17% and 34% for the CRT and SBRT arms, respectively. The sample size for the phase III study is 228. Multiple sensitivity analyses will also be performed to further evaluate the results: (i) complete case analysis that excludes those with missing/inevaluable; (ii) multiple imputation analysis that assigns different portions of those missing/inevaluable to be either responders or non-responders. A secondary “as treated” sensitivity analysis will be performed to include only eligible patients who have received protocol-assigned radiation therapy.

Table: Sample Size Parameters for a Subsequent Randomized Controlled Trial

| CRT response | SBRT response | Effect size | Drop-out rate | Total Sample Size |
|--------------|---------------|-------------|---------------|-------------------|
| 10 | 30 | 20 | 0.1 | 160 |
| 10 | 30 | 20 | 0.05 | 152 |
| 15 | 35 | 20 | 0.1 | 186 |
| 15 | 35 | 20 | 0.05 | 176 |
| 20 | 40 | 20 | 0.1 | 206 |
| 20 | 40 | 20 | 0.05 | 194 |
| 25 | 45 | 20 | 0.1 | 220 |
| 25 | 45 | 20 | 0.05 | 210 |
| 30 | 50 | 20 | 0.1 | 230 |
| 30 | 50 | 20 | 0.05 | 218 |
| 10 | 25 | 15 | 0.1 | 252 |
| 10 | 25 | 15 | 0.05 | 238 |
| 15 | 30 | 15 | 0.1 | 298 |
| 15 | 30 | 15 | 0.05 | 284 |
| 20 | 35 | 15 | 0.1 | 338 |
| 20 | 35 | 15 | 0.05 | 320 |
| 25 | 40 | 15 | 0.1 | 370 |
| 25 | 40 | 15 | 0.05 | 350 |
| 30 | 45 | 15 | 0.1 | 392 |
| 30 | 45 | 15 | 0.05 | 372 |

This table shows potential sample sizes for the planned RCT study with two-sided alpha = 0.05 and power = 80%. The sample size is very sensitive to the CRT response rate. For example, for an effect size of 20%, if the response rate with CRT is 10%, the sample size will be 160 patients while if the response rate is 30%, the sample size will increase to 230.

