10.1.1 Evaluable for Complete Pain Response to Radiotherapy

All patients who have received at least one dose of radiotherapy and provide complete worst pain score information for the treated site of radiation treatment and opioid analgesic intake information at baseline and at least the 3 month follow up contact will be considered evaluable for response to radiotherapy. Patients will have response classified according to the definitions in Section 10.2.1.

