## **2.5 Efficacy**

### **2.5.1 Definitions and Variables**

#### **2.5.1.1 Complete pain response in the treatment area at 3 months post-radiation**

All patients who have received at least one dose of radiotherapy and provide complete worst pain score information for the treated site of radiation treatment and opioid analgesic intake information at baseline and at least the 3 month follow up contact will be considered evaluable for response to radiotherapy.

A Complete Pain Response is defined as a pain score of zero (0) at the treated site with no concomitant increase in analgesic intake (stable or reducing analgesics in daily oral morphine equivalent). The response status at 3-month and 6-month will be derived by comparison of worst pain score and analgesic intake at the time point to baseline data. As a sensitive analysis, the response status will be derived from comparison of worst pain score and analgesic intake at the time point to day 0 data prior to RT, and perform the similar analyses.

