#### **Sensitivity analyses:**

- A sensitivity analysis for the complete pain response rate will be performed with the per protocol population in evaluable patients. (table 12b)

**Subgroup analysis:** the primary analysis on primary endpoint will be performed based on patients' stratification factors at baseline, i. e. Histology (radioresistant vs. radiosensitive) And "Mass"\* on imaging (present vs. absent) (Table 14) with interaction p-value to tell if any differential treatment effect across levels of stratification factors.

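### The inevaluable class includes patients whose complete-response status is known (early deaths, and recorded pain of 1 or more with opioid data missing), and the missing-data sensitivity analyses treat them as unknown.

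*Protocol*

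**What the plan says.** **Evaluability.** Under Protocol 10.1.1, repeated in SAP 2.5.1.1, a patient must have had at least one radiotherapy dose and must "provide complete worst pain score information for the treated site of radiation treatment and opioid analgesic intake information at baseline", and again at the 3-month contact. SAP 2.5.1.4 sets the same rule at 6 months.

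**Endpoint.** "A Complete Pain Response is defined as a pain score of zero (0) at the treated site with no concomitant increase in analgesic intake" (SAP 2.5.1.1; same definition in Protocol 10.2.1).

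**Primary analysis.** Protocol 14.2 counts patients who are inevaluable through missing data as non-responders. SAP 2.5.2.1 divides by all randomized patients.

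**Sensitivity analyses.** Protocol 14.3 lists (i) a complete-case analysis that leaves out the missing or inevaluable patients and (ii) a "multiple imputation analysis that assigns different portions of those missing/inevaluable to be either responders or non-responders". The SAP's list has one entry: "A sensitivity analysis for the complete pain response rate will be performed with the per protocol population in evaluable patients" (Table 12b). SAP 2.5.1.1 adds a repeat against Day 0 data, and SAP 2.5.2.1 an unadjusted chi-square. The SAP does not describe any imputation.

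**Reporting.** SAP Table 11 gives reasons for inevaluability by arm. SAP Table 12 has five rows: CR, PR, SD, PD and Inevaluable.

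**The concern.** The evaluability rule suits the four-category response, where opioid data are needed to separate partial response, stable pain and progression. It does not suit the binary primary endpoint. A 3-month worst pain score of 1 or more rules out complete response whatever the opioid entry says, and a patient who has died by then cannot have one. Both are certain non-responders. Table 12 gives them no row but Inevaluable, because stable pain is reserved for evaluable patients.

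A missing-data check should vary only what is unknown. As worded, the complete-case and evaluable analyses remove known failures from the denominator, and the imputation may turn some of them into responders. The first raises response rates and can move the arm difference if deaths or blank medication tables are unbalanced. The second can make a sound result look fragile. Table 11 would show the reasons, but no analysis uses them.

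**Working it through.** **Inputs (Protocol 14.3 unless stated)**
- "Sample size estimate for the phase III controlled trial is with a two-sided 5% level test and 80% power"
- "we estimate the complete pain responses will be 20% for the CRT and 40% for the SBRT treatment arms, respectively"
- Allowance for inevaluable patients: 15%, not split by cause or arm
- "we expect the complete pain response rates for the intent-to-treat analysis to be 17% and 34% for the CRT and SBRT arms, respectively"; that is, 0.85 × 20% = 17% and 0.85 × 40% = 34%
- Total N 228, allocated 1:1 (SAP 1.1), so 114 per arm
- f, the share of inevaluable patients who are known failures: not in the documents, so taken over 0% to 100%

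**1. Reproduce the plan's figure.** Pooled two-proportion formula, p̄ = 0.255, d = 0.17:

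n₀ = [1.96·√(2·0.255·0.745) + 0.8416·√(0.17·0.83 + 0.34·0.66)]² / 0.17² ≈ 102.0

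Continuity correction: n = (n₀/4)·[1 + √(1 + 4/(n₀d))]² ≈ 113.5, so 114 per arm and 228 in total. This matches. The whole class is already counted as failing, so N does not depend on f.

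**2. Complete-case difference, equal inevaluable rates.** As written: 40.0% − 20.0% = 20.0 points. With known failures kept in the denominator, each arm's rate is its ITT rate divided by (0.85 + 0.15f), so the difference is 0.17/(0.85 + 0.15f):

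| f | CRT | SBRT | Difference (points) |
|---|---|---|---|
| 0% | 20.0% | 40.0% | 20.0 |
| 25% | 19.2% | 38.3% | 19.2 |
| 50% | 18.4% | 36.8% | 18.4 |
| 75% | 17.7% | 35.3% | 17.7 |
| 100% | 17.0% | 34.0% | 17.0 |

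The inflation is at most 20.0 − 17.0 = 3.0 points, reached only if every inevaluable patient is a known failure.

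**3. Unequal splits (assumed), whole patients.** 0.34 × 114 ≈ 39 SBRT responders, 0.17 × 114 ≈ 19 CRT responders, 0.15 × 114 ≈ 17 inevaluable per arm, so 97 evaluable per arm. Unstratified Pearson tests:

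| Known failures put back | SBRT | CRT | Difference (points) | p |
|---|---|---|---|---|
| None (as written) | 39/97 | 19/97 | 20.6 | 0.0017 |
| 8 SBRT, 8 CRT | 39/105 | 19/105 | 19.0 | 0.002 |
| 12 SBRT, 4 CRT | 39/109 | 19/101 | 17.0 | 0.006 |
| 4 SBRT, 12 CRT | 39/101 | 19/109 | 21.2 | 0.0006 |

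The 20.6 differs from the 20.0 in step 2 only because responders are rounded to whole patients.

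Unequal inevaluable rates also matter. Hold the ITT rates at 17% and 34% and let all inevaluables be known failures. The complete-case difference is then 0.34/0.80 − 0.17/0.90 = 23.6 points with 10% CRT and 20% SBRT inevaluable, and 0.34/0.90 − 0.17/0.80 = 16.5 points with the rates reversed.

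**4. Imputation.** ITT: 39 v 19 of 114, p = 0.002. Score k CRT inevaluables as responders and no SBRT:
- k = 6: 39 v 25, p = 0.039
- k = 7: 39 v 26, p = 0.057
- k = 17: 39 v 36, p = 0.67

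If known failures are fixed as non-responders, k cannot exceed about 17(1 − f). At f = 50% that is about 8 (p = 0.080); at f = 75%, about 4 (39 v 23, p = 0.017). The extreme difference against SBRT is 0.17 − 0.15(1 − f): 2.0, 5.8, 9.5, 13.3 and 17.0 points at f = 0, 25, 50, 75 and 100%.

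**The case against.** Several points on the other side stand.

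- **Only supporting analyses are touched.** A reader might infer that the trial's conclusion is at risk. The documents do not support that: the primary rule already counts these patients as non-responders, and no complete-case scenario above changes the conclusion. In one of them the analysis as written understates the difference (20.6 against 21.2).
- **Scoring the dead as responders is permitted, not planned.** A reader might infer that the plan does this. Protocol 14.3(ii) only fails to exclude it, and the SAP has no imputation at all. Under the SAP as written, only the evaluable-patient part of the point operates.
- **The 7-patient tipping case is a one-sided extreme.** It needs 7 CRT and no SBRT inevaluables scored as responders. If 4 SBRT inevaluables are scored too, it takes 11 CRT (43 v 30 of 114). The test is unstratified and follows a single fill-in; it is neither the planned stratified test nor a pooled multiple-imputation result.
- **Response among those assessed is a legitimate supporting quantity.** The 20% and 40% planning rates are of that kind. A version that excludes deaths is defensible if labelled as such.
- **The pain-recorded, opioid-missing group may be small.** Both items come from one diary (Protocol Appendix VII), and staff usually fill in the medication names beforehand.

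These points limit the weight. They do not justify treating a recorded pain score of 1 or more as an unknown complete-response status, or leaving death open to imputation as response.

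**Conclusion.** The point holds for the sensitivity analyses only. The evaluability rule, read with the definition of complete response, puts known non-responders in the inevaluable class; this follows from the rules and from Table 12, although neither document says so in words. At planning values with equal inevaluable rates, the complete-case difference is inflated by 0 to 3 points, depending on f. Unequal splits can move it either way. The imputation is the more exposed check, because its message can depend on whether known failures are held fixed: in the worst case p is 0.67 if all 17 CRT inevaluables are imputable and 0.017 if only about 4 are.

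These sizes assume the planning rates, 114 per arm and an f that the documents do not give. The change should be made because the rule misclassifies patients and the data to correct it are already collected: pain in the diary, and deaths within the 6-month period on the case report forms (Protocol Appendix IV).

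**What to change.** For the complete-response endpoint at 3 and 6 months, in Protocol 10.1.1 and 14.3 and SAP 2.5.1.1, 2.5.1.4, 2.5.2.1 and 2.5.2.2:

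1. Add a derived flag for determinate non-responders: death before the assessment, or recorded pain of 1 or more at the assessment whatever analgesic data are missing.
2. Carry the 14.3(ii) imputation into the SAP with flagged patients fixed as non-responders, so that only unknown status is imputed.
3. In the complete-case and evaluable analyses (Table 12b), keep patients with recorded pain of 1 or more in the denominator as non-responders.
4. Report the complete-case result with deaths counted as non-responders. Label any version without deaths as response among assessed survivors.
5. Show determinate and indeterminate patients separately in Table 11.

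Limit the pain rule to complete response. SAP 2.5.2.3 repeats these analyses for overall (CR/PR) response, and pain of 1 or more does not rule out a partial response.

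Cost: one derived variable, SAP wording and a little more analysis work. Complete-case response rates will be slightly lower. No new data or patients are needed.
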